**Michigan Mental Health Integration Partnership - Implementing PTSD Treatment in Federally
Qualified Health Centers for Michigan Medicaid Enrollees
PE-PC Pilot**

National Clinical Trial Number: NCT03711266

Date: September 23, 2021

Principal Investigator:

[name], Assistant Professor, University of Michigan Department of Psychiatry

Supported by:

Michigan Mental Health Integration Partnership (MIP) Scholars program
Michigan Department of Health and Human Services

PROTOCOL SUMMARY

Title:	PE-PC Pilot
Study Description:	A study to evaluate the delivery and sustainability of a brief trauma-focused treatment, Prolonged Exposure for Primary Care (PE-PC), an evidence-based intervention for PTSD, delivered via telehealth to patients in Community Health Centers (CHCs) in Michigan.
Outcomes:	
Primary Outcome: PE-PC participants will experience reductions in PTSD symptoms as measured by the PTSD Checklist for DSM-5 (PCL-5) at 2 months and 4 months.
 
Secondary Outcomes: PE-PC participants will experience reductions in depression as measured by the PHQ-9 at 2 months and 4 months. We will also examine the mechanisms of PE-PC's effect by measuring the two potential mediators of intervention effectiveness, recovery goals (Recovery Assessment Scale; RAS) and posttraumatic cognitions (Post-Traumatic Cognitions Inventory; PTCI).

Intervention Information:	Deliver PE-PC to patients via telehealth. This treatment consists of four 30-minute sessions of in-vivo and narrative exposure, with content drawn from the PE model. ¹
Study Population:	The sample will consist of 50 participants, age 18 and older, of any gender, race or ethnicity, who are currently enrolled at a CHC and screen positive for PTSD on the PCL-5 (PCL-5 \geq 33).
Locations:	University of Michigan Family Medical Center of Michigan Hamilton Community Health Network Family Health Care
Estimated Study Start Date:	October 1, 2018
Study Duration:	2 years

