1 BACKGROUND & RATIONALE

1.1 Background

Posttraumatic stress disorder (PTSD) is a disorder that develops following exposure to traumatic events such as rape, assault, natural disaster, or combat. It is associated with distress, impairment, and greater risk for adverse health outcomes, including among Michigan Medicaid enrollees.² The percentage of patients screening positive for PTSD in primary care settings has been estimated to range from 14%-23%.³⁻⁶

Despite this high prevalence, treatment for PTSD is severely limited at CHCs.⁷ In addition, patients with PTSD may be reluctant to seek care in specialty mental health clinics.⁸ Furthermore, community mental health providers rarely have training in efficacious PTSD treatments, and community dissemination and implementation efforts have had mixed success.⁹ Thus, there is significant need for a brief PTSD treatment delivered in the primary care setting. Providing brief PTSD treatment in the primary care setting aligns with the MDHHS Section 298 Initiative to coordinate physical health services and behavioral health services.

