2 OUTCOMES

2.1 Primary Outcome

The Primary Outcome measure is change in PTSD symptoms as measured by the PTSD Checklist for DSM-5 (PCL-5). PCL-5 will be administered at baseline, 2-months post-enrollment (around the time of treatment completion) and 4-months post- enrollment. Two 2-month and 4-month surveys will be administered regardless of whether the patient has completed the intervention.

1. PCL-5 [Time Frame: Baseline, 2-months, 4-months]

The PCL-5¹¹ is a 20-item self-report measure designed to assess PTSD symptoms as defined by the DSM-5. Each item of the PCL-5 is scored on a five point scale ranging from 0 ("not at all") to 4 ("extremely"). The PCL-5 has strong internal consistency, test-retest reliability, and convergent and discriminant validity.^{12,13} Scores ≥ 33 indicate a probable diagnosis of PTSD.

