3 STUDY DESIGN

The goal of this pilot project is to deliver PE-PC to 50 patients via telehealth and evaluate patients' engagement with the treatment, satisfaction, and PTSD-related outcomes. This is an open trial. All participants will receive the same intervention.

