4.1 Inclusion Criteria

The goal of the study inclusion and exclusion criteria is to identify a broadly representative sample of CHC patients with PTSD.

Patients will be eligible for the study if they:

- 1) are age 18 years or older
- 2) receive care at a Michigan CHC
- 3) have a PCL-5 score ≥ 33
- 4) have had psychotropic medication stability for at least 4 weeks

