4.2 Exclusion Criteria

Patients will be excluded if they are: 1) substantially cognitively impaired, 2) unable to agree to study procedures for any reason (including incompetency), 3) at high risk of suicide, or 4) currently engaged in a trauma-focused behavioral treatment (such as Prolonged Exposure or Cognitive Processing Therapy). Patients who do not speak English will be excluded for logistical reasons.

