5.3 Delivery of Treatment

Eligible participants are individuals presenting in CHCs who screen positive for PTSD, using validated screening measures currently used in multiple Michigan CHCs. Those who screen positive will be connected by a warm handoff to the research assistant (or will call us after being provided with our contact information), who will review inclusion/exclusion criteria, present the study information sheet, and schedule the first meeting with the telepsychologist.

PE-PC treatment will follow the PE-PC manual and patient workbook. Treatment content for PE-PC is drawn from the PE model and condensed so as to deliver the most efficacious components of PE. PE-PC consists of four, 30-minute appointments scheduled approximately once a week over 4-6 weeks (to accommodate scheduling and missed appointments). Before beginning the 4-session treatment, the telepsychologist will schedule an initial appointment with the patient to determine the index trauma and answer any questions about the treatment. During the first PE-PC session, the PC-MHI provider will review the “Confronting Uncomfortable Memories” activity workbook to be completed at home and brought back for use in subsequent sessions. The workbook asks the patient to write a detailed first-person narrative of the event associated with the greatest level of current distress, including recollection of personal thoughts, feelings, and physical reactions. Emotional processing questions are also included. In addition, the telepsychologist will plan for in-vivo exposure activities between sessions. The patient will be instructed to complete the memory exposure for 30 minutes each day between sessions. At the second PE-PC session, the telepsychologist will review the patient’s exposures, problem-solve any implementation difficulties, and process the exercises. The patient will then read the narrative and his or her answers to the emotional processing questions out loud and they will process the exercise. Practice continues between sessions. This session format and content are repeated at the third and fourth sessions. At the end of the fourth session, the telepsychologist and patient will review treatment progress assisted by results of the PTSD Checklist for DSM-5 (PCL-5) administered during the fourth session. Participants who still need or desire treatment at the conclusion of PE-PC will receive referrals to other mental health resources.

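### Does referral to other care at the end of PE-PC undermine the 4-month primary PCL-5 result?

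*Combined protocol and SAP*

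**What the plan says.** The primary outcome in the Protocol Summary is that "PE-PC participants will experience reductions in PTSD symptoms as measured by the PTSD Checklist for DSM-5 (PCL-5) at 2 months and 4 months". Section 2.1 defines it as change in PCL-5, with surveys at 2 and 4 months after enrollment whether or not the participant finished PE-PC. It places the 2-month survey at about the end of treatment.

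Two entry rules concern other care. Section 4.1 requires that patients "have had psychotropic medication stability for at least 4 weeks", and section 4.2 excludes those "currently engaged in a trauma-focused behavioral treatment".

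Section 5.3 schedules PE-PC over 4-6 weeks after an initial appointment and then says: "Participants who still need or desire treatment at the conclusion of PE-PC will receive referrals to other mental health resources".

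Section 6 names paired t-tests, multiple regression and multiple imputation. It says nothing about treatment received after entry, and sections 2.1 and 2.2 list no measure of it. Section 3 describes an open trial in which everyone receives the same intervention.

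**The concern.** The plan appears to restrict other care at the start and then arrange it before a primary assessment. A participant who does poorly on PE-PC, is referred and improves elsewhere would add to the 4-month reduction. The Protocol Summary also speaks of how PE-PC works, "by measuring the two potential mediators of intervention effectiveness", and section 2.2 measures those mediators at 4 months as well. A reader could therefore take the 4-month score as the lasting effect of PE-PC alone when part of it may come from something else, and the plan does not commit to showing how many participants had other care.

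**Working it through.** The plan gives no figure to reproduce: N = 50 is stated without power, standard deviation or dropout. The check covers timing, then size, then whether a different analysis would do better.

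**Timing.** One month is 365.25/12/7 = 4.35 weeks, so 2 months is 8.7 weeks and 4 months is 17.4 weeks.
- If the 4-6 week course starts at enrollment, it ends 17.4 - 6 = 11.4 to 17.4 - 4 = 13.4 weeks before the 4-month score, and 8.7 - 6 = 2.7 to 8.7 - 4 = 4.7 weeks before the 2-month score.
- With a lead-in of 0-4 weeks before the first session (assumed), the course ends at weeks 4-10. The gap to 4 months is then 7.4 to 13.4 weeks, and the gap to 2 months runs from +4.7 to -1.3 weeks.
- If treatment ends at 2 months, as section 2.1 suggests, the window is 17.4 - 8.7 = 8.7 weeks.

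Referral therefore precedes the 4-month score on schedule, and it may precede the 2-month score too. The two visits differ in degree only.

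**Size.** Shift in the mean 4-month change = share with other care × extra gain among them. Both inputs are assumed.
- 1 of 50 with 5 points: 0.02 × 5 = 0.1. 5 of 50 with 10 points: 0.10 × 10 = 1.0.
- 10 of 50 with 5 to 10 points: 0.20 × 5 = 1.0 to 0.20 × 10 = 2.0.
- Wide range, 10-50% with 5-15 points: 0.10 × 5 = 0.5 to 0.50 × 15 = 7.5.
- Standard error of a mean change, for an assumed SD of change of 12-16: 12/√50 = 1.70 to 16/√50 = 2.26.
- Participants with other care needed for a shift of one standard error: 1.70/10 × 50 = 8.5 to 2.26/5 × 50 = 22.6, so about 9 to 23 of 50.

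Section 1.1 says "treatment for PTSD is severely limited at CHCs" and that patients may be reluctant to use specialty clinics. That points to the lower end, but does not establish it.

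**Would another analysis do better?** The main alternative sets scores after other care to missing and imputes them. A simulation used these assumed inputs: n = 50; 4,000 runs; 10 imputations; SD 12 at baseline and 16 later; correlation 0.4 between baseline and later scores and 0.6 between session four and 4 months; extra gain 7.5; uptake log-odds of 1 per SD. Errors are measured against a world without other care. At 10% uptake:
- Observed scores overstate the reduction by 0.10 × 7.5 = 0.75 points, whatever drives uptake.
- Imputation using the session-four PCL-5 is nearly unbiased if uptake follows that score, but overstates by 0.9 points if uptake follows the later symptom course.

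The alternative can thus be worse than the plan, and the data cannot show which case applies. The 0.75 counts as an error only against a no-other-care target that the plan never adopts. Measured as change from baseline, the observed scores carry no such bias.

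**The case for a change.** The strongest case for a change is about transparency. With no comparator, a count of participants who had other PTSD treatment or a medication change is one of the few aids a reader would have. The survey rule in section 2.1 covers non-completion of PE-PC, not other care. Section 1.2 cites an earlier randomized trial whose gains lasted to 6 months, so a reader might carry that reading over to this 4-month score. The documents give no uptake figure, so a large shift cannot be ruled out.

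Each of these statements is correct, but they support only a sentence in the report:
- The apparent contradiction between entry rules and referral is weaker than it looks. Section 4.1 gives the purpose of the criteria as a broadly representative clinic sample. They bar only recent medication change and current trauma-focused therapy, so stable medication and other therapy are allowed.
- Section 1.2 describes another study, and the plan makes no maintenance claim for its own result.
- The mediator language goes beyond what one arm can support at either visit, with or without referral.
- Relabelling the 4-month result as PE-PC followed by referral would be less accurate than the plan's wording. Referral depends on need or wish, and the surveys include people who did not finish PE-PC.
- The data may already exist. Section 3 promises to evaluate "engagement with the treatment, satisfaction, and PTSD-related outcomes", and sections 2.1 and 2.2 list no measure for the first two of these either, so the listed outcomes are not the whole survey.

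**Conclusion.** No change to the plan. The silence on later care is real, but analysts can fill it sensibly: report change in PCL-5 from baseline at each visit, regardless of completion or later care, and mention other care where it is known or say that it was not collected. The planned tests and all observed scores stay as they are.

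The shift is probably 0.1 to 1.0 point, below one standard error of 1.7 to 2.3. This rests on assumed uptake of 1 to 5 of 50, an assumed gain of 5 to 10 points and an assumed SD of change of 12 to 16. The conclusion does not depend on the shift being small. Even at the assumed extreme of 7.5 points, the paired change remains a correct description of what happened to these participants, and attribution to PE-PC would be no better supported without referral. It would need another look only if the report presented the 4-month score as the effect of PE-PC alone.

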6 STATISTICAL ANALYSIS

We used paired t-tests and multiple regression to determine symptom change over time. Multiple imputation was used to impute missing data. Ten imputed datasets were generated, and coefficients and standard errors were adjusted for the variability between imputations according to Rubin’s combination rule.¹⁹ We included auxiliary variables that were correlated with the missing variables at $r > 0.4$.²⁰ Imputation procedures were conducted in SAS, using the Markov Chain Monte Carlo approach.

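### Do two unranked PCL-5 time points and two listed methods leave the primary result with inflated error?

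*Combined protocol and SAP*

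**What the plan says.** The Protocol Summary gives the primary outcome as "reductions in PTSD symptoms as measured by the PTSD Checklist for DSM-5 (PCL-5) at 2 months and 4 months". Section 2.1 describes the same measure as change in PCL-5, taken at baseline, "2-months post-enrollment (around the time of treatment completion) and 4-months post- enrollment". Neither place ranks the two follow-ups or says whether one or both must show a reduction.

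Section 6 states: "We used paired t-tests and multiple regression to determine symptom change over time". The rest of that section concerns multiple imputation. It gives no alpha, sidedness, test order, regression model or assignment of methods to outcomes.

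Two other passages bear on the 4-month score. Section 5.3 says: "Participants who still need or desire treatment at the conclusion of PE-PC will receive referrals to other mental health resources". Section 2.1 says the "4-month surveys will be administered regardless of whether the patient has completed the intervention". Section 3 describes an open trial with a single intervention: "The goal of this pilot project is to deliver PE-PC to 50 patients via telehealth".

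**The concern.** Two time points and two methods could yield up to four p-values for one primary hypothesis. If any of them could carry the claim, the chance of a false claim would exceed the nominal level and the reader could not tell which result was planned.

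The two time points also seem to answer different questions. Two months falls near the end of treatment. By 4 months some patients may have taken up referrals, so a late improvement might owe something to other care.

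Finally, a regression of symptoms on time that treated three scores from one patient as independent would misstate the standard error of within-patient change and could disagree with the t-test.

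The stake is the pre-post PCL-5 change, which is the whole efficacy result in a trial without a control arm.

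**Working it through.** **Inputs.** Two follow-up times (Protocol Summary, Section 2.1), two methods (Section 6) and n = 50 (Section 3). The plan states no alpha, effect size, SD or between-visit correlation, so there is no figure of its own to reproduce. Two-sided 0.05 per test is assumed and the correlation is varied.

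**Step 1: two time points, one test each.** For independent tests, P(either) = 1 − 0.95² = 0.0975. For correlated tests, P(either) comes from the bivariate normal, and P(both) = 0.05 + 0.05 − P(either). With no true change at either time point:

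| Correlation of the two changes | Either suffices | Both required |
|---|---|---|
| 0 | 0.0975 | 0.0025 |
| 0.3 | 0.0951 | 0.0049 |
| 0.5 | 0.0907 | 0.0093 |
| 0.7 | 0.0835 | 0.0165 |
| 0.9 | 0.0704 | 0.0296 |

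If one time point has a true change and the other has none, the both-required rule is wrong only when the null one rejects, which has probability at most 0.05. So the error is 7.0% to 9.8% under one rule and never above 5% under the other. The plan adopts neither expressly, and its wording joins the time points with *and*.

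**Step 2: adding the second method.** Four independent tests would give 1 − 0.95⁴ = 0.185. That overstates the case, because both methods use the same data. A simulation of paired t-tests plus a regression with time and patient effects (n = 50, no missing data, 20,000 runs per scenario) gave 0.097 to 0.127 for any of the four. Part of the upper end arises because that regression pools one variance over visits, and its own per-test error ranged from about 0.03 to 0.094. These figures need both methods applied to the PCL-5 at each visit, which Section 6 does not say. A regression of change scores on patient characteristics, one row per patient, fits the sentence equally well and has no repeated rows.

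**Step 3: the standard-error criticism.** Suppose visits were pooled as independent, with equal variances and between-visit correlation ρ. The variance of mean change is 2σ²(1 − ρ)/n, but the model would use 2σ²/n. The standard error is then too large by 1/√(1 − ρ): 1.41 at ρ = 0.5 and 1.83 at ρ = 0.7.

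- False positives: the true threshold becomes 1.96 × 1.41 = 2.77 or 1.96 × 1.83 = 3.58 standard errors, so the error is about 0.6% or 0.03%.
- Power: an effect with 80% paired power lies 1.96 + 0.84 = 2.80 standard errors from zero. The distances to the threshold are 2.80 − 2.77 = 0.03 and 2.80 − 3.58 = −0.78, giving power of 51% and 22%.

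Such a model would lose power and add almost nothing to family-wise error. It cannot be counted as a further source of inflation.

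**Step 4: all four scales.** Eight independent tests (four scales, two times) give 1 − 0.95⁸ = 0.337. This merges primary and secondary outcomes into one family. The Protocol Summary presents RAS and PTCI as possible mediators. The figure does not measure error in the PCL-5 claim.

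**Step 5: referral care.** Section 5.3 places the four sessions over 4 to 6 weeks after an initial appointment. Two months is between 8 and 9 weeks, so a patient who started promptly could finish and be referred before the 2-month survey. The overlap with other care is therefore not confined to 4 months. Uptake is unknown, and Section 1.1 says that PTSD treatment at these centers is scarce and that patients may be reluctant to use specialty clinics. Surveying everyone regardless of completion is consistent with reading the score as the outcome after being offered PE-PC, including whatever care follows, although the plan does not say so.

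**The case for a change.** The strongest case for acting is that silence is itself the defect. The word *and* may only list measurement times, not set a joint requirement. With no control arm, the PCL-5 change is all the efficacy evidence there is. Naming one time point, a fixed test order and one repeated-measures model would be mostly wording, would need no extra patients and would cap primary error at 5%.

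The omissions are real, and that part stands. The remedies are less clear-cut:

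- **Primary time point.** Two months is closest to treatment effect. Four months better serves an interest in durability, which Section 1.2 raises by citing maintained gains in the earlier randomized trial. Either is defensible.
- **Timing.** The Protocol Summary gives an October 2018 start and two years' duration. The document is dated September 2021, and Section 6 is in the past tense. A ranking written now might not be prospective, and an added survey question on other treatment is probably no longer possible.
- **Splitting by later treatment.** Reporting 4-month change by whether patients sought other care conditions on something that happens after treatment. It would not isolate the effect of PE-PC.
- **Mixed model.** It is a reasonable alternative to t-tests on imputed data, but not a correction of them.
- **What alpha control would protect.** Entry requires a PCL-5 of at least 33, so regression to the mean may produce some average fall without any treatment effect. The zero-change null is then a weak benchmark, and strict control against it adds little to interpretation.

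**Conclusion.** No change to the plan follows. It leaves unwritten which time point leads, whether both must succeed, and which method serves the PCL-5. At an assumed two-sided 0.05 this could matter by 2 to 5 percentage points of error for the two time points (7.0% to 9.8% against 5%), but only under an either-one rule that the plan does not state. If both are required, the error stays at or below 5%.

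The regression criticism depends on an assumed model that would be conservative. The referral point depends on unknown uptake and could touch the 2-month score as well.

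In an uncontrolled pilot of 50, analysts fill this gap in the ordinary way: they report both time points with the method behind each, and note that care after referral may contribute to the follow-up scores. The conclusion rests on both time points being reported. If only the more favorable one appeared, the concern about selective reporting would have force.

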1 BACKGROUND & RATIONALE

1.1 Background

Posttraumatic stress disorder (PTSD) is a disorder that develops following exposure to traumatic events such as rape, assault, natural disaster, or combat. It is associated with distress, impairment, and greater risk for adverse health outcomes, including among Michigan Medicaid enrollees.² The percentage of patients screening positive for PTSD in primary care settings has been estimated to range from 14%-23%.³⁻⁶

Despite this high prevalence, treatment for PTSD is severely limited at CHCs.⁷ In addition, patients with PTSD may be reluctant to seek care in specialty mental health clinics.⁸ Furthermore, community mental health providers rarely have training in efficacious PTSD treatments, and community dissemination and implementation efforts have had mixed success.⁹ Thus, there is significant need for a brief PTSD treatment delivered in the primary care setting. Providing brief PTSD treatment in the primary care setting aligns with the MDHHS Section 298 Initiative to coordinate physical health services and behavioral health services.

